8.1 Screening

Screening

Investigators may re-screen a participant only once if the investigator is reasonably certain that reasons for screen failure will be resolved prior to or during a repeat screening attempt. Reasons to re-screen may include but are not limited to the following:

- Laboratory value(s) out of range due to sampling error or that might be within range after medically-appropriate supplementation
- The participant has a medical condition that can be stabilized or resolved prior to the repeat screening attempt
- Additional time is required following the participant's last dose of an excluded medication (see Table 6-2)

A participant must provide a new informed consent prior to the initiation of any re-screening procedures (e.g. participant must be reconsented). A new subject number will be assigned.

8.1.1 Eligibility screening

8.1.1.1 Hepatitis screen, HIV screen

Not applicable.

8.1.1.2 Alcohol test, Drug screen, Urine cotinine

Participants will be tested for substances of abuse (e.g. alcohol, amphetamines, barbiturates, benzodiazepines, cannabinoids, cocaine and opiates).

Positive results will not be exclusionary if the participant doesn't meet DSM-5 criteria for substance use and inclusion would be the responsibility of the Investigator.

This will be recorded as source data only by the use of an "S" for the corresponding criteria in Table 8-1 (Assessment Schedule) of the protocol.

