Oral and Systemic Hormonal Contraceptives for contraception purposes	From Baseline and up to 1 week after study drug injection	Do not administer study treatment	Not accepted as highly effective contraception until a dedicated clinical study shows no drug-sruf interaction between MIJ821 and hormonal contraceptives.
Systemic Corticosteroids	Chronic use is prohibited from Screening and until the end of study	Do not administer study treatment	Safety (additive cardiovascular and neuropsychiatric effects)
Cough decongestants	Within 12 hours prior to study drug injection and up to at least 4 hours after end of study drug injection	Do not administer study treatment	Safety (additive sedative effects) and confounding effect for safety assessments
Benztropine and diphenhydramine	Within 12 hours prior to study drug injection.	Do not administer study treatment	Safety (additive sedative effect) and confounding

Medication	Prohibition period	Action taken to study treatment**	Reason
	Continuous use is prohibited.		effect for safety assessments
Benzodiazepines	Within 12 hours prior to and 4 hours after study drug injection	Do not administer study treatment	Safety (adding sedative effect and confounding effect for safety assessments)
Trazodone	Within 24 hours prior to and 24 hours after study drug injection	Do not administer study treatment	Safety (additive Risk of QT prolongation)
Alcohol	Within 24 hours prior to and 24 hours after study drug injection*	Do not administer study treatment	Safety (additive sedative and CNS effects), confounding effect for safety and efficacy assessments
Cannabis, medical marijuana and psychostimulants (amphetamines, methylphenidate, modafanil, armodafinil etc.)	Within 24 hours prior to each study visit and 24 hours after study drug injection*	Do not administer study treatment	Safety (additive CNS effects), confounding effect for safety and efficacy assessments
Opioids	Within 24 hours prior to each study visit and 24 hours after study drug injection*	Do not administer study treatment	Safety (additive sedative and CNS effects), confounding effect for safety and efficacy assessments

^{*} In case of a prohibited use or when a participant appears intoxicated at the visit (e.g., alcohol, etc.), visit reschedule should be considered as per the permitted visit window

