6.2.4.1 Dietary restrictions and smoking

No dietary or smoking restrictions in this study.

Participants should not consume alcohol or cannabis 24 hours before each study visit. If the participant appears intoxicated at the visit (e.g., alcohol, marijuana, other agent), a visit reschedule should be considered.

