As per Section 4.6, during a Public Health emergency as declared by Local or Regional authorities i.e. pandemic, epidemic or natural disaster that limits or prevents on-site study visits, alternative methods of providing continuing care may be implemented by Novartis as the situation dictates. If permitted/approved by local or Regional Health Authorities and Ethics Committees as appropriate and depending on operational capabilities, phone calls, virtual contacts (e.g. tele consult) or visits by site staff/ home nursing staff to the participant's home, can replace on-site study visits, for the duration of the disruption until it is safe for the participant to visit the site again.

Table 8-1 Assessment Schedule

Table 0-1	A336331	1101		JOHICO	iuic															
Period	Screening					Trea	tment						Follow-up							
Visit Name	Screening									Follow- up call	Follow- up visit	Follow- up call	Follow- up visit	Follow- up call		Follow- up call				
Visit Numbers ¹	1					20						40	50	60	70	80	90	100	110	120
Days	-28 to -1					1						2	4	8	11	15	18	22	25	29
Time (post-dose)	-	- 1h	0h	0.17h	0.33h	0.5h	0.75h	1h	1.5h	2h	4h	24h	•	-	-	-	-	-	-	-
Informed consent	Х																			
Inclusion / Exclusion criteria	Х	Х																		
Medical history/current medical conditions	×																			
SCID-5	S ³																			
MGH-ATRQ	S ³																			
Alcohol Test and Drug Screen	S ³	S ³																		
Pregnancy and assessments of fertility ⁴	Х	X ⁵																		х
Demography	Х																			
Body Height	Х																			
Body Weight	Х	Х																		Х
Physical Examination	S ³																			S ³

Period	Screening					Trea	tment									Follo	w-up			
Visit Name	Screening									Follow- up call	Follow- up visit	Follow- up call	Follow- up visit	Follow- up call	Follow- up visit	Follow- up call				
Visit Numbers ¹	1					20						40	50	60	70	80	90	100	110	120
Days	-28 to -1					1						2	4	8	11	15	18	22	25	29
Time (post-dose)	-	- 1h	0h	0.17h	0.33h	0.5h	0.75h	1h	1.5h	2h	4h	24h	-	-	-	-	-	-	-	-
Body Temperature	Х	X										Х								Х
Blood Pressure and Pulse Rate	Х	X ⁶				Х			Х		X	Х		X		Х		Х		Х
Respiratory rate ³	S	ഗ				S			S		S	S		S		S		S		S
Oxygen Saturation						S ^{3,7}	,													
Electrocardiogram (ECG)	Х	X ⁶				Х			Х		X	Х								Х
CADSS		Χ				Х			Х		Χ	Χ		Х		X		X		Х
MOAA/S		Χ				Х			Х		Χ	Χ		Х		Х		Х		X
Memory Assessment Questions ¹³						S					S	s								
C-SSRS	Χ	Х									Х	Х		Х		Х		Х		Χ
Local tolerability assessment						S					S	s								

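### For a Day 1 breathalyser, the rule in Protocol Section 8.1.1.2 that a positive alcohol test is not exclusionary conflicts with Table 6-2 and exclusion 20, and refers to neither

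*Protocol*

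**What the plan says.** Protocol Section 8.1.1.2 treats alcohol and drugs together. It begins "Participants will be tested for substances of abuse (e.g. alcohol, amphetamines", then lists further drug classes. Its rule is that "Positive results will not be exclusionary if the participant" does not meet DSM-5 criteria for substance use, and that "inclusion would be the responsibility of the Investigator". It does not separate one test time from another.

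The row "Alcohol Test and Drug Screen" in Table 8-1 is marked at screening and on Day 1 at -1 h, both times as source documentation only. Randomisation stands in the same -1 h column. Table 8-3 gives a breathalyser for alcohol and a dipstick for drugs.

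Table 6-2 (Section 6.2.2) prohibits alcohol "Within 24 hours prior to and 24 hours after study drug injection". The action column says that study treatment is not to be given. The reason column reads "Safety (additive sedative and CNS effects), confounding effect for safety and efficacy assessments". The asterisk on that row says that, after prohibited use or apparent intoxication, "visit reschedule should be considered as per the permitted visit window". Section 6.2.4.1 adds "Participants should not consume alcohol or cannabis 24 hours before each study visit" and likewise asks only that rescheduling be considered when a participant appears intoxicated.

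Exclusion 20 in Section 5.2 excludes participants taking anything prohibited under Section 6.2.2. Section 6.4.2 has the IRT contacted only after the inclusion and exclusion criteria are confirmed.

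**The concern.** A single rule has been written for two tests that answer different questions. At screening, a positive alcohol test says little about the participant's state at dosing, and leaving the matter to DSM-5 status and the investigator is reasonable. At -1 h on Day 1, the question is whether to inject a drug with known sedative and dissociative effects into someone who has just tested positive for alcohol. Table 6-2 answers no. Section 8.1.1.2, which is where a site would look up what to do with the result, says that it does not exclude the participant and hands inclusion to the investigator.

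A site that follows 8.1.1.2 alone could dose someone whom the protocol's own safety table bars. The stakes are that participant's safety and the sedation (MOAA/S) and dissociation (CADSS) data, both of which are secondary safety endpoints. A site that applies Table 6-2 only when the syringe is ready would have a participant who is randomised but undosed, whom Section 8.1.2 classes as an early terminator.

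**Working it through.** The plan states no figure on this point, so the main check compares the texts.

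**Timing.** Screening runs from Day -28 to Day -1, roughly 24 to 672 h before dosing (28 x 24 = 672). The Day 1 test is at -1 h, so 24 - 1 = 23 of the 24 barred pre-dose hours have already passed. I assume that a positive breath test reflects drinking within those 23 hours; the documents give no detection window for the device. On that assumption, a positive Day 1 result shows use inside the Table 6-2 window.

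**Rules that apply to a positive Day 1 breathalyser.**

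| Source | What it tells the site |
|---|---|
| Section 8.1.1.2 | Not exclusionary if DSM-5 criteria are not met; investigator decides on inclusion |
| Table 6-2, action column | Withhold study treatment |
| Table 6-2 asterisk; Section 6.2.4.1 | Consider rescheduling |
| Exclusion 20 with Section 6.4.2 | Not eligible, so the IRT should not be contacted |
| Table 8-1, footnote 3 | Addresses a positive drug screen only; silent on alcohol |
| Table 8-3 footnote | Clinical confirmation of prohibited use, for urine dipsticks only |

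**Does the DSM-5 condition reconcile them?** No. The SCID-5 is given at screening only and concerns a disorder. A participant without a disorder can still have been drinking the evening before dosing, and 8.1.1.2 calls that result non-exclusionary.

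**How are other -1 h tests handled?** In Table 8-1, footnote 5 makes dosing conditional on a negative urine pregnancy test, and footnote 6 makes it conditional on blood pressure and ECG results that satisfy the investigator. The alcohol test has no such gate.

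**Would a slip be visible?** The result is not entered in the eCRF, and the intercurrent-event review in SAP Section 2.4.2.2 looks for onset after dosing. Alcohol taken before dosing falls outside that review. It would have to be picked up as a protocol deviation, for example through the full eligibility verification in Protocol Section 11.3.

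**Size.** The documents give no rate of positive Day 1 breathalysers. I assume a range of p = 0.5% to 3%, with n = 56 and 14 per arm (Protocol Section 12.8.1).

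- Expected positive tests, n x p: 56 x 0.005 = 0.28; 56 x 0.03 = 1.68.
- Chance of at least one positive test, 1 - (1 - p)^56: 0.24 at p = 0.005; 0.82 at p = 0.03.
- Weight of one participant in an arm: 1/14 = 7.1 percentage points of any MOAA/S or CADSS category proportion.

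**The case against.** The strongest reply is that both rules can be obeyed. Section 8.1.1.2 sits under eligibility screening and can be read as saying only that a positive test does not remove someone from the study, while Table 6-2 decides whether to inject that day. A site would then keep the participant, withhold the dose and reschedule. On this view the asterisk concerns what happens to the visit and leaves the action column unconditional. Exclusion 20, the check in Section 6.4.2 and the Section 3 requirement to review Day 1 evaluations against eligibility before dosing all point the same way, and a protocol need not repeat every rule in every section.

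Much of this stands. A careful site would not dose, and the protocol cannot fairly be said to permit dosing after a positive Day 1 breathalyser. A reader might infer that from 8.1.1.2 alone, but Table 6-2 and exclusion 20 forbid it. The eligibility-versus-dosing split does not fully work, however. Exclusion 20 makes the contents of Table 6-2 an eligibility matter, so calling the result non-exclusionary still clashes with it. The split is also nowhere stated, and randomisation happens in the same -1 h column as the test.

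A reader might also extend the point to drug screens, because footnote 3 of Table 8-1 allows randomisation after a positive one. The documents do not support that. A dipstick does not date use, and the Table 8-3 footnote already sends the question of prohibited use to Sections 6.2.1 and 6.2.2, with clinical confirmation.

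**Conclusion.** The point holds for alcohol on Day 1. Section 8.1.1.2 conflicts with Table 6-2 and exclusion 20 for a positive breathalyser at -1 h. The latter two should govern, but 8.1.1.2 does not refer to them. It is worth correcting because the matter is dosing safety and the correction is short.

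The size is small. Under the assumed 0.5% to 3% rate, 0.3 to 1.7 positive tests would be expected. The 24% to 82% is the chance of at least one positive test. A reader might take it as the chance of wrongful dosing, but that would also require a site to pass over Table 6-2, exclusion 20 and the Section 6.4.2 check, and nothing in the documents gives a probability for that. The 7.1 points apply only if a dosed participant's sedation or dissociation category were changed by alcohol. With so few participants potentially affected, the effect on the 24 h MADRS analysis is negligible.

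**What to change.** In Section 8.1.1.2, limit the non-exclusionary rule for alcohol to the screening test. There, or as a Table 8-1 footnote in the style of footnotes 5 and 6, state that Table 6-2 governs the Day 1 result and is applied before randomisation: after a positive Day 1 breathalyser the participant is not randomised or dosed that day, and the visit is rescheduled within the 28-day screening period with the -1 h assessments repeated. The repeat should include the MADRS, since inclusion 4 requires a score of at least 24 before randomisation on Day 1 and the baseline is the last value before injection (SAP Section 2.1.1.2).

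Footnote 3 on drug screens needs no change.

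The cost is one or two sentences, carried in a protocol amendment under Section 14.1, and an occasional rescheduled visit. If the screening period runs out, the single re-screen in Section 8.1 is available; its listed reasons already include needing more time after an excluded medication. No sample size, endpoint or analysis changes. The gain is participant safety and cleaner sedation and dissociation data.

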8.1.2 Information to be collected on screening failures

Participants who sign an ICF and subsequently found to be ineligible prior to randomization will be considered a screen failure. The reason for screen failure should be recorded on the appropriate CRF. The demographic information, informed consent, and the Inclusion/Exclusion pages must also be completed for screen failure participants. No other data will be entered into the clinical database for participants who are screen failures, unless the participant experienced a SAE during screening phase (see SAE Section 10.1.3 for reporting details). If the participant fails to be randomized, the IRT must be notified within 2 days of the screen fail that the participant was not randomized.

Participants who are randomized and fail to start treatment, e.g. participants randomized in error will be considered an early terminator. The reason for early termination should be recorded on the appropriate CRF.

8.2 Participant demographics/other baseline characteristics

Country-specific regulations should be considered for the collection of demographic and baseline characteristics in alignment with CRF.

Participant demographic, socio-economical and baseline disease characteristic data will be collected on all participants. Relevant medical history/current medical conditions present prior to signing the informed consent will be recorded. Investigators have the discretion to record abnormal test findings on the medical history eCRF, if in their judgment, the abnormality occurred prior to the informed consent signature.

Participant demographics: full date (if permitted) or year of birth, sex, race/predominant ethnicity (if permitted) and relevant medical history/current medical conditions (until date of signature of informed consent) will be recorded in the eCRF. Where possible, the diagnosis and not symptoms should be recorded. Participant race/ethnicity data are collected and analyzed to identify any differences in the safety and/or efficacy profile of the treatment due to these characteristics. In addition, we need to assess the diversity of the study population as required by Health Authorities.

All prescription medications, over-the-counter drugs and significant non-drug therapies prior to the start of the study must be documented. See the protocol Section 6.2.1 Concomitant Therapy for further details on what information must be recorded on the appropriate page of the eCRF.

8.3 Efficacy

8.3.1 Handling of Efficacy Assessments by Independent Site Raters

The primary efficacy endpoint of MIJ821 compared with placebo is assessed based on the MADRS scale, SIGMA version.

Administration of MIJ821 is associated with a number of transient adverse events, including sedation, dissociative symptoms, memory gaps/amnesia and cardiovascular events. To minimize the risk of introducing bias, trained and qualified site personnel will perform efficacy and safety assessments. Independent site raters who perform the MADRS, will be different from those who evaluate vital signs, adverse events, ECG results, MOAA/S, CADSS and C-SSRS. Independent site raters for the MADRS, are not allowed to access or review participants safety records and, therefore, must not provide clinical care for participants. Clinical care of participants will be performed by the investigator or delegate at the study site who are not MADRS,

Whenever possible, all efforts should be made to use the same independent raters for the MADRS, at each site to assess the same participant throughout the study. If this is not possible, review of the appropriate prior assessments and communication with prior raters should be conducted, as needed. Any clinically relevant safety findings from the scales or the interviews must be communicated to the investigator.

During the study, the roles of the investigator and the independent site rater, including their back-ups, are not interchangeable at the participating sites.

8.3.2 Montgomery Asberg Depression Rating Scale (MADRS), SIGMA version

The Montgomery Asberg Depression Rating Scale (MADRS, SIGMA version) is a clinician-rated scale designed to measure depression severity and detects changes due to antidepressant treatment: the test consists of 10 items, each of which is scored from 0 (item not present or normal) to 6 (severe or continuous presence of the symptoms), for a total possible score of 60. Higher scores represent a more severe condition. The MADRS evaluates apparent sadness, reported sadness, inner tension, sleep, appetite, concentration, lassitude, interest level, pessimistic thoughts and suicidal thoughts (Khan et al 2002). The test exhibits high inter-rater reliability. In this study, the following recall periods will be used: "Last 7 days with euthymic baseline", "over the past 4 hours", "Last 7 days", and "Since last evaluation" for the primary endpoint. Whenever possible, the MADRS should be administered by the same rater to assess the same participant throughout the study.

8.3.3 Appropriateness of efficacy assessments

The MADRS is a standard scale used for registration studies of depression. It is relatively quick to administer, does not focus predominately on the somatic symptoms of depression, but rather addresses core mood symptoms such as sadness, tension, lassitude, pessimistic thoughts, and suicidal thoughts. The MADRS is sensitive to change from treatment effects over time, and is considered a gold standard registration scale for depression.

8.4 Safety

Safety assessments are specified below with the assessment schedule detailing when each assessment is to be performed.

For details on AE collection and reporting, refer to AE section.

As per Section 4.6, during a Public Health emergency as declared by Local or Regional authorities i.e. pandemic, epidemic or natural disaster, that limits or prevents on-site study visits, regular phone or virtual calls can occur (every week or more frequently if needed) for safety monitoring and discussion of the participant's health status until it is safe for the participant to visit the site again.

Table 8-2 Assessment Specification

Assessment	Specification
Physical examination	A complete PE will include the examination of general appearance, skin, neck (including thyroid), eyes, ears, nose, throat, lungs, heart, abdomen, back, lymph nodes, extremities, vascular, and neurological. If indicated based on medical history and/or symptoms, rectal, external genitalia, breast, and pelvic exams will be performed. A complete PE will be at screening and end of study visits. Information for all PEs must be included in the source documentation at the study site. Clinically relevant findings that are present prior to signing informed consent must be recorded on the appropriate CRF that captures medical history. Significant findings made after signing informed consent which meet the definition of an AE must be recorded as an AE.

Assessment	Specification
Vital signs	Vital signs will include the collection of body temperature (recorded in °C), BP and pulse measurements and respiratory rate. Body temperature can be otic or oral according to local practice, but the same type of measurement should be used for the same participant at every assessment. After the participant has been resting in supine position for 5 minutes systolic and diastolic BP will be measured using an automated validated device with an appropriately sized cuff. In case the cuff sizes available are not large enough for the participant's arm circumference, a sphygmomanometer with an appropriately sized cuff may be used. BP will be measured following ECG measurements. Clinically notable values of BP or pulse (see Exclusion Criteria Section 5.2 and Section 3) need to be confirmed by a repeated measurement 2-5 minutes after the first measurement. In case of repeated vital assessments, the eCRF should contain all assessments at any time point (including screening, baseline and post-dose time points).
Height and weight	Height is obtained in centimeters (cm) and body weight is obtained in kilograms (kg) and rounded to the nearest 0.1 kg, and will be measured at screening and baseline. Weight is obtained in indoor clothing, without shoes, and repeated at baseline.

8.4.1 Laboratory evaluations

All abnormal lab results must be evaluated for criteria defining an adverse event and reported as such if the criteria are met. For those lab adverse events, repeated evaluations are mandatory until normalization of the result(s) or until the result is no longer considered to be clinically significant.

Clinically significant abnormalities must be recorded on the relevant section of the medical history/eCRF page as appropriate. Clinically notable laboratory findings are defined in Appendix 1 (Section 16.1).

A central laboratory will be used for analysis of all specimens collected. Details on the collections, shipment of samples and reporting of results by the central laboratory are provided to investigators in the laboratory manual.

In the case where a laboratory range is not specified by the protocol, but is outside the reference range for the laboratory at screening, a decision regarding whether the result is of clinical significance or not shall be made by the Investigator and shall be based, in part, upon the nature and degree of the observed abnormality. The assessment may be repeated once prior to randomization.

In all cases, the Investigator must document in the source documents, the clinical considerations (i.e., result was/was not clinically significant and/or medically relevant) in allowing or disallowing the subject to continue in the study.

Clinically relevant deviations of laboratory test results occurring during or at completion of the study must be reported and discussed with Novartis personnel. The results should be evaluated for criteria defining an adverse event and reported as such if the criteria are met.

Repeated evaluations are mandatory until normalization of the result(s) or until the change is no longer clinically relevant. In case of doubt, Novartis personnel should again be contacted.

Fasting considerations:

The participants must be fasting at screening in order to measure fasting glucose. In case the sample was not taken in a fasted state, a repeat sample should be taken at Day 1 after the

participant has been fasting overnight. For the subsequent visits, all participants must also be fasting overnight. If not, no repeat sample will be taken.

Table 8-3 Clinical laboratory parameters collection plan

Table 0-3	Chilical laboratory parameters collection plan
Test Category	Test Name
Hematology	Hemoglobin, hematocrit, red blood cell count, white blood cell (WBC) count with differential (e.g., neutrophils, basophils, eosinophils, monocytes, lymphocytes), other (absolute value preferred and percent) and platelet count will be measured.
Chemistry	Albumin, alkaline phosphatase, total bilirubin, bicarbonate, calcium, Total cholesterol, low density lipoprotein (LDL), high density lipoprotein (HDL), chloride, creatinine (Glomerular Filtration Rate to be calculated based on the Cockcroft-Gault formula), creatinine kinase (CK), Gamma-glutamyl transferase (GGT), glucose (fasting), lactic dehydrogenase (LDH), phosphorus, lipase, amylase, magnesium, potassium, total protein, AST, ALT, sodium, triglycerides, blood urea nitrogen (BUN) or Urea, uric acid, C-reactive protein (high sensitivity). If the total bilirubin concentration is increased above 1.5 times the upper limit of normal, direct and indirect reacting bilirubin should be differentiated. Thyroid Stimulating Hormone (TSH) level will be analyzed as well. In case of clinically relevant abnormal TSH value, additional evaluation will be performed (free triiodothyronine [fT3] and free thyroxine [fT4]).
Urinalysis	A midstream urine sample (approx. 30 mL) will be obtained, in order to avoid contamination with epithelial cells and sediments, and allow proper assessments. A semi-quantitative "dipstick" evaluation for the following parameters will be performed: specific gravity, pH, glucose, protein, bilirubin, urobilinogen, ketones, leukocytes and blood. If the dipstick result is positive for protein, leucocytes and/or blood, the sample will be sent for microscopic analysis of WBC, RBC and casts. Furthermore the protein-creatinine ratio (PCR) and the albumin-creatinine ratio (ACR) might also be measured
Coagulation	Prothrombin time/International normalized ratio (PT/INR), Activated partial thromboplastin time (APTT)
Alcohol / Drugs of Abuse*	Breathalizer / Dipstick
Pregnancy Test and Assessment of Fertility	Serum / Urine pregnancy test (as outlined in Section 8.4.3)

^{*} Since urine dipsticks are neither quantitative nor sensitive enough to detect the exact timeframe when a drug was used, if a urine dipstick result is positive for a drug(s) of abuse, the prohibited use (as defined in Section 6.2.1 and Section 6.2.2) should be further confirmed by the treating physician by means of a clinical assessment and data obtained from the participant or his/her relatives. The investigator judgment prevails in case of contradictory data or results.

